4.2. Removal of Participants from Therapy or Assessment

Participants are free to discontinue trial participation at any time. Withdrawal from the trial will not affect or prejudice participants further care or treatment. In addition, participants may be withdrawn from study treatment and assessments at any time, if deemed necessary by the PI or Sponsor.

Potential reasons for withdrawal of participants from this study include, but are not limited to:

- The participant withdraws his or her consent (defined as a participant who explicitly takes back his or her consent)
- The PI considers it, for safety and/or study compliance reasons, in the best interests of the participant that he or she be withdrawn
- Initiation of concomitant medication prohibited by the study protocol (see [Table 2](#))
- Initiation of psychotherapy in psychotherapy naïve participants at baseline
- Discontinuation of psychotherapy in participants receiving therapy at baseline
- Pregnancy
- Participant is lost to follow-up (defined as a participant who fails to comply with scheduled study visits or contact, who has not actively decided to withdraw from the study, and for whom no alternative contact information is available [this implies that at least two attempts have been made to contact the participant])
- Any center personnel break the randomization code for that participant
- The participant attempts suicide or is at significant risk of suicide (either in the opinion of the investigator or defined as a “yes” to suicidal ideation questions 4 or 5 or answering “yes” to suicidal behavior on the C-SSRS during the study)

The reason and date the participant is withdrawn from the study and further treatment with the IMP will be documented in the electronic case report form (eCRF) (e.g., lost to follow-up, consent withdrawn, incorrect enrollment, AEs, etc.).

If a participant is withdrawn from the study, the PI should attempt to complete all study assessments in [Table 1](#) for the EoS Visit.

Participants who withdraw due to an AE should be followed until resolution of the AE, or the PI or delegated center personnel decides that the AE is stable, and the participant does not need further follow-up. All AEs should be followed up according to Section 8 [ADVERSE EVENTS](#).

If a participant is withdrawn from the study, all data collected until the time of withdrawal will be included in the analyses.

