7.2.9. Columbia Suicide Severity Rating Scale (C-SSRS)

The Columbia Suicide Severity Rating Scale (C-SSRS) is a ClinRO administered in a semi-structured interview format, designed to evaluate suicide risk by assessing and tracking suicidal ideation and

behavior (Posner *et al.*, 2011). The C-SSRS identifies specific behaviors which may be indicative of an individual's intent to complete suicide. The C-SSRS has five-questions addressing suicidal ideation, five-sub-questions assessing the intensity of ideation, and four-questions addressing suicidal behavior. The scale should be administered by a certified rater and all positive scores should receive a careful clinical review to determine if intervention is needed. This instrument demonstrated good convergent and divergent validity with other suicidal ideation and behavior scales and has high sensitivity and specificity for suicidal behavior classifications. Both the ideation and behavior subscales are sensitive to change over time. The intensity of ideation subscale demonstrated moderate to strong internal consistency (Posner *et al.*, 2011).

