5.2.10 Columbia-Suicide Severity Rating Scale

The C-SSRS results will be listed.

The following items will be summarized by treatment and visit:

- Number and percentage of patients who answered at least one of the questions 1 and 2 with “yes” under Suicidal Ideation
- Number and percentage of patients answering each of the questions 1 to 5 with “yes”
- For the patients who answered “yes” to questions 1 and 2:
 - Number and percentage in each category (1 to 5) for most severe suicide ideation
 - Answers (number and percentages per answer) to the Intensity of Ideation questions
- Number and percentages for the answers to the questions under Suicidal Behavior
- Number of actual suicide attempts

The same table – especially the number and frequency of patients who committed actual suicide attempts since the last visit – is used for the evaluation of C-SSRS as an exploratory efficacy endpoint.

Responses to each item will be listed by patient.

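### SAP 5.2.10 limits the C-SSRS severity and intensity rows to patients with yes to both questions 1 and 2, so category 1 is always empty and some patients with ideation drop out of those rows

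*SAP*

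**What the plan says.** SAP 5.2.10 lists the C-SSRS items to be summarised by treatment and visit. Three bullets matter here.

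- The opening bullet: "Number and percentage of patients who answered at least one of the questions 1 and 2 with “yes” under Suicidal Ideation".
- The next bullet counts yes answers to each of the five ideation questions, with no restriction on who is counted.
- The third bullet sets a condition, "For the patients who answered “yes” to questions 1 and 2", and places two summaries under it: "Number and percentage in each category (1 to 5) for most severe suicide ideation" and "Answers (number and percentages per answer) to the Intensity of Ideation questions".

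Further bullets cover suicidal behaviour and actual attempts, again unrestricted, and item responses are listed by patient. The section adds that the same table serves C-SSRS as an exploratory efficacy endpoint.

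On the scale itself, Protocol 7.2.9 says: "The C-SSRS has five-questions addressing suicidal ideation". Protocol 4.2 treats a yes "to suicidal ideation questions 4 or 5 or answering" yes to suicidal behaviour as marking significant risk. Protocol 9.3.6 asks only for listings and descriptive summaries by arm and visit. Neither document defines the population of the severity and intensity summaries anywhere else.

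**The concern.** Within one list the SAP uses two conditions on the same pair of questions: an explicit either-or, then a plain conjunction. A programmer who sees that contrast has good reason to code OR for the opening bullet and AND for the third.

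The conjunction does not fit the table beneath it. The table has a row for category 1, yet a patient whose worst answer is question 1 has said no to question 2 and cannot meet the condition. The condition also removes patients who say no to question 1 and yes to something more severe.

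C-SSRS is a safety endpoint and, through this table, an exploratory efficacy endpoint, in a disorder where the protocol describes suicidality as common. A severity distribution that lacks its lowest category, and an unknown part of the higher ones, does not describe ideation in either arm. A patient who moves from category 2 to category 1 would leave the severity rows instead of moving down within them.

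**Working it through.** The plan gives no figure to reproduce. The check is logical.

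**Inputs.** Five yes/no ideation questions (Protocol 7.2.9); the two conditions and the category range 1 to 5 (SAP 5.2.10). One inference is needed, because the documents do not define the categories: category k means that question k is the highest question answered yes.

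**Step 1: the category 1 row.** Category 1 requires no to questions 2 to 5. The condition requires yes to question 2. Both cannot hold, so the row is zero by construction.

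**Step 2: all answer patterns.** Five yes/no questions give 2^5 = 32 patterns. By category:

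| Condition | 1 | 2 | 3 | 4 | 5 | Total |
|---|---|---|---|---|---|---|
| Yes to both 1 and 2 (third bullet as written) | 0 | 1 | 1 | 2 | 4 | 8 |
| Yes to 1 or 2 (opening bullet) | 1 | 2 | 3 | 6 | 12 | 24 |
| Left out by the third bullet | 1 | 1 | 2 | 4 | 8 | 16 |
| Yes to any of 1 to 5 | 1 | 2 | 4 | 8 | 16 | 31 |

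The last row is 2^(k-1) patterns for category k, and 1 + 2 + 4 + 8 + 16 = 31. The 31 - 24 = 7 further patterns have no to questions 1 and 2 but yes to a higher one.

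**Step 3: if questions 3 to 5 are asked only after a yes to question 2.** The documents do not describe skip rules, so this is an assumption. The opening bullet then admits 17 patterns (1, 2, 2, 4, 8), the third bullet still admits 8, and 17 - 8 = 9 are left out (1, 1, 1, 2, 4). Category 1 is again empty. Yes to any of questions 1 to 5 also gives 17, so the two wider conditions coincide.

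**Step 4: higher ideation among those left out.** No to question 1, yes to question 2, and yes to 4 or 5: question 3 is free (2 ways) and questions 4 and 5 have 3 qualifying combinations, so 2 x 3 = 6 patterns. All 6 are left out, with or without the skip rule.

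These are counts of possible patterns. They are not expected patient numbers.

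**Step 5: effect on the percentages.** At one visit, let N be the patients assessed, I those with any ideation, h those in category 4 or 5, o those with ideation who are left out, and d those left out who are in category 4 or 5.

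- With SAP 4.2's default denominator (patients with data at the time point), the figure shown is (h - d)/N instead of h/N: unchanged if d = 0, too low otherwise.
- With the restricted group as denominator, it is (h - d)/(I - o) instead of h/I. This is too high when d/o < h/I and too low when d/o > h/I.

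SAP 5.2.10 does not say which denominator applies, and the documents give no value for d, o, h or I.

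**The case against.** The strongest reply is that this is loose drafting. The opening bullet and the 1-to-5 range both suggest that either-or was meant, and a careful programmer might read it that way. That is probably the intention, but the text does not say so, and a literal reading produces a defective table. It is a reason to correct the wording.

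The reply is also right that little is lost overall. A reader might infer that a patient who moves from no ideation to category 1 disappears from the analysis. That is not so: the patient is counted in the opening bullet, in the question 1 row and in the listing. A fall from category 2 to 1 shows as a drop in the question 2 count.

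A reader might also infer that the category 4 to 5 percentages are inflated. If 20% to 50% of patients with ideation were in category 1 only (an assumption with no source in the documents), the factor would be 1/(1 - 0.2) = 1.25 to 1/(1 - 0.5) = 2. This needs the restricted group as denominator and d = 0. SAP 4.2's default removes the inflation, and omitted patients with higher ideation pull the other way.

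Finally, a reader might call the lack of an any-time post-baseline summary an error, since a patient withdrawn for ideation or behaviour contributes to few visits. The documents do not support that. Protocol 9.3.6 asks for by-visit summaries. Protocol 4.2 gives potential reasons for withdrawal, so leaving is not automatic, and it asks for an End of Study visit. SAP 4.2 maps early-termination and unscheduled assessments to the nearest scheduled visit, with a worst-case rule for safety data when several fall in one window.

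**Conclusion.** The point holds as a wording defect with a definite consequence in two descriptive summaries. Followed as written, the category 1 row is zero in both arms at every visit. Patients with yes to only one of questions 1 and 2 are missing from the severity and intensity rows, including some with yes to question 4 or 5. This rests on reading the conjunction literally and on category k meaning question k as the highest yes.

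The number of patients affected cannot be derived from the documents, and the direction of any bias in the severity percentages is undetermined. All these patients remain in the listings and in the per-question, behaviour and attempt rows; those with yes to question 1 or 2 also remain in the opening count. No primary analysis is affected. The correction should be made because the rule as stated gives a wrong table and is simple to put right.

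**What to change.** In SAP 5.2.10, change the condition on the third bullet to patients who answered yes to at least one of questions 1 to 5. State the denominator for the rows beneath it: either all patients assessed at the visit, which is the SAP 4.2 default, or patients with any ideation at that visit. One sentence defining the severity category as the highest question answered yes would remove the remaining inference. The cost is a line or two of SAP text and a table-shell edit; no new data are needed.

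An optional addition is one row per arm for the worst post-baseline ideation category and any post-baseline suicidal behaviour. SAP 5.2.4 already plans across-visit summaries for laboratory values. C-SSRS is scheduled at every visit, so this costs one extra table row from data already collected.

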5.2.11 Safety Monitoring (Data Monitoring Committee [DMC])

A data monitoring committee (DMC) will be established to monitor the safety and efficacy data generated during the study. The DMC will consist of three independent clinical specialists. The DMC will review accumulated data from the ongoing study. Based on these reviews, the DMC will advise on the further conduct of the study. An independent unblinded off site statistician will present safety outputs to the DMC and conduct an interim analysis for futility or sample size recalculation, see Section 4.8. The composition, activities, and responsibilities of the DMC is described separately in the DMC charter.

The following displays will be prepared for each regular DMC meeting:

- Disposition Table, as specified in the SAP, but also showing number of patients currently still on treatment
- Overall summary of Adverse Events
- Summary of Adverse Events by System Organ Class, Preferred Term and Treatment
- Summary of Compliance for Drug Intake
- Listing of Serious Adverse Events
- Listing of Adverse Events
- Listing of Abnormal Laboratory Values
- Listing of Columbia-Suicide Severity Rating Scale results

Details will be given in a separate IDMC TFL Shell document.

5.3 Other Analyses

The analysis of biomarker and genotyping data will be done at a later time and are not described in this SAP.

5.3.1 Pharmacokinetics

Pharmacokinetic concentrations will be listed by patient. The listing is based on the SAF, but patients excluded from the PPS will be flagged.

Summary statistics for the active treatment will be produced using the PPS.

Spaghetti plot and mean plots of concentrations versus visit will be displayed. The SAF will be used for individual concentrations and the PPS will be used for means.

When calculating means for figures and summary statistics values below the lower limit of quantification (BLQ values) will be replaced with 0.

For US Sites only, a sampling at around Tmax to assess average levels and help drug monitoring will be conducted in a patient subpopulation (approximately 10 patients). If Cmax values observed are in the range of those seen in healthy volunteers, no further samples should be necessary at Tmax. In this selected subpopulation, PK assessments will be obtained at Visits 4 and 6 (in addition to the pre-dose sample already scheduled on these visits as per the original protocol). This analysis will be described in detail in a separate SAP.

5.3.2 Pharmacodynamics

Target engagement (LSD-TE1) will follow the analysis for PK described in Section 5.3.1. In addition, LSD-TE1 is used in exposure analysis (see Section 5.2.1).

5.3.3 Visit to Health Care Services

The number of visits to primary care services, mental health services, emergency room services and the overall number of visits to any health care services in the month prior to the Visit will be summarized descriptively by Visit and treatment.

In addition, the number and frequency of patients for each reason of visit will be summarized. For post-baseline Visits, the change from baseline for the number of visits by type of service and reason will be calculated and included in the summary. The number and frequency of patients having visited health care services at least once will also be summarized by visit, type of service and reason for visit.

The total number of visits by type of services will be calculated for each patient across all Study Visits. As an exploratory analysis only, the Mann-Whitney test will be used to compare the total number between the two treatment arms. Only patients who do not discontinue early will be included in this analysis.

A listing by patient will be produced showing the number of visits and the reason for the visits.

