5.4. Post-study Access to IMPs

Post-study access to the IMP will not be available.

6. Prior and Concomitant Therapy

Prior medication is defined as medication received prior to first IMP intake. Any medication received at least once after the first IMP intake will be considered as concomitant medication.

All prior medications taken within four weeks prior to screening will be recorded in the eCRF at Visit 1.

Concomitant medication will be recorded in the concomitant medication log/page of the eCRF throughout the study. Prior to initiating a new concomitant medication, participants should check with their study doctor.

Participants will be asked to maintain a stable regimen of background pharmacological therapy, not to initiate any prohibited medications during the trial and to advise their study physician of any medication changes throughout the study.

Psychotherapy treatment should also be registered in the eCRF.

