6.1.1. Permitted/Prohibited psychotherapy

Considering that psychotherapy is the standard of care for BPD, all enrolled participants will need to maintain their pre-screening psychotherapy schedule throughout the trial duration. Participants entering the study cannot start any type of psychotherapy within 3 months prior to enrollment or throughout the trial duration.

Specifically, participants receiving psychotherapy before initiating the study need to remain in psychotherapy throughout the trial. However, those participants not receiving psychotherapy before the study should not initiate psychotherapy during the trial. Participants deemed needing immediate or emergent psychotherapy and those initiating psychotherapy during the study will be discontinued from the trial.

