7.2.10. Number of visits to healthcare services outside of the trial

The use of health care resources, including all the participant visits to primary care, mental health and emergency care services, will be recorded at each study visit, starting at baseline as described in [Table 1](#) and Section 7.7. The number of visits to healthcare services outside of the trial (primary care, mental health services & ER visits) will be evaluated '*in the last month*' at Baseline Visit as well as at Visit 4, Visit 6 and Visit 8/EoS.

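### The exploratory test of mental-health visits (SAP 5.3.3) appears to count psychotherapy sessions that patients must keep unchanged, which dilutes any treatment effect by an amount the documents do not fix

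*SAP*

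**What the plan says.** **What is counted.** Protocol 7.2.10 defines healthcare use as "including all the participant visits to primary care, mental health and emergency care services, will be recorded at each study visit". The recall period is the last month, asked at baseline and at Visits 4, 6 and 8. No text in either document says whether a routine psychotherapy session is a mental-health visit.

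**What is held constant.** Protocol 6.1.1 states that "all enrolled participants will need to maintain their pre-screening psychotherapy schedule throughout the trial duration". It adds that "participants receiving psychotherapy before initiating the study need to remain in psychotherapy throughout the trial", and that "those participants not receiving psychotherapy before the study should not initiate psychotherapy during the trial". Patients who start psychotherapy are discontinued. Protocol 4.2 lists, among potential reasons for withdrawal, "Discontinuation of psychotherapy in participants receiving therapy at baseline".

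**What is tested.** SAP 5.3.3 first names what is summarised at each visit: primary care, plus "mental health services, emergency room services and the overall number of visits to any health care services". For the comparison it forms each patient's total by type of service across all study visits. The comparison is labelled exploratory: "the Mann-Whitney test will be used to compare the total number between the two treatment arms". Patients who leave the trial early are left out of it. No stratum, covariate or baseline adjustment is named.

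**What else is recorded.** The reason for each visit is collected, and SAP 5.3.3 uses it in descriptive summaries and a listing. Protocol section 6 says "Psychotherapy treatment should also be registered in the eCRF". SAP 5.1.1 already carries psychotherapy at baseline (yes/no) as a factor in the primary model.

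**The concern.** A psychotherapy session outside the trial is, in ordinary language, a visit to a mental-health service. If sessions are counted, the mental-health total has two parts. One part, unscheduled or other mental-health contacts, could fall under an effective treatment. The other is set by the patient's existing schedule, which the protocol asks them to keep.

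The scheduled part can be large: weekly sessions over 12 weeks give 12 visits. It is also close to zero in everyone not in psychotherapy. A rank test on the sum then spends many of its between-arm comparisons on pairs of patients whose order is decided by psychotherapy status, and those pairs carry no information about treatment.

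The risk is a null comparison of mental-health use that says little about the drug. Protocol synopsis, Overall Study Design, says the trial is meant to inform later trials, so such a null could be over-read.

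**Working it through.** **The plan's own figure.** No power, visit rate or effect is stated for this test. The only stated sample size is for the primary endpoints (SAP 4.7): effect size 0.51, two-sided alpha 0.025, 80% power. The formula n = 2(2.241 + 0.842)²/0.51² gives 73.1, so 74 per arm. The plan uses 75, and 75/0.8 = 93.75, so 94 per arm and 188 enrolled. This reproduces. I take 75 completers per arm for the visit test, because it is restricted to patients who do not discontinue early.

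**Inputs that must be assumed.** The documents do not give the share p of patients in psychotherapy, the session frequency, or the rate of other visits. I varied p from 10% to 90%. Sessions were weekly, every two weeks, monthly or mixed in frequency. Other visits had a mean of 2, 3 or 6 in 12 weeks (negative binomial, shape 1). The treatment rate ratio was set so that a two-sided 5% Mann-Whitney test on the other visits alone has about 80% power. There were 2,000 runs per setting.

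**Analytic check.** Suppose every patient in psychotherapy has a higher total than every patient not in it. Pairs with different psychotherapy status then favour neither arm on average. Only same-status pairs carry the effect, and their proportion is p² + (1−p)². The null variance of the rank sum is unchanged apart from ties, so the noncentrality shrinks by that factor. Power of 80% at two-sided 5% corresponds to 1.96 + 0.84 = 2.80.

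| p | p² + (1−p)² | noncentrality | power |
|---|---|---|---|
| 10% | 0.82 | 2.30 | Φ(0.34) = 63% |
| 20% | 0.68 | 1.90 | Φ(−0.06) = 48% |
| 30% or 70% | 0.58 | 1.62 | Φ(−0.34) = 37% |
| 50% | 0.50 | 1.40 | Φ(−0.56) = 29% |

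**Simulation, power with sessions counted (reference about 80%).**

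| Sessions | Other visits, mean | Share p | Power |
|---|---|---|---|
| Weekly (12) | 2–3 | 10% | 63–64% |
| Weekly (12) | 2–3 | 30% | 35–39% |
| Weekly (12) | 2–3 | 50% | 28–33% |
| Weekly (12) | 2–3 | 70% | 36–42% |
| Weekly (12) | 6 | 10–90% | 44–67% |
| Every two weeks | 2–6 | 10–90% | 38–74% |
| Monthly | 2–3 | 30–70% | about 56–71% |
| Monthly | 2–6 | 10–90% | 56–78% |

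A further run let near-weekly sessions vary between 10 and 13 per patient, with a mean of two other visits and a rate ratio of 0.5 (1,500 runs). It gave 36%, 25% and 29% at shares of 30%, 50% and 70%. The range for weekly sessions at those shares is therefore about 25–42%.

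With mixed frequencies, power was 36–69% at shares of 10–30% and 17–46% at shares of 50% or more.

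Psychotherapy status explained between 6% and 76% of the variance of the ranks. With no treatment effect and sessions counted, the rejection rate was 5.1%.

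**The remedies.** Removing the sessions returns power to the reference by construction. The table shows a van Elteren test stratified by psychotherapy at baseline, with a mean of 3 other visits, a rate ratio of 0.5 and reference power of 85–86%.

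| Sessions | Share p | Unstratified | Stratified |
|---|---|---|---|
| All weekly | 20 / 50 / 80% | 55 / 36 / 55% | 85 / 87 / 85% |
| Frequency varies | 20 / 50 / 80% | 59 / 31 / 26% | 77 / 61 / 48% |

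If sessions turn out not to be in the count, stratifying costs about one percentage point.

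**The case against.** The strongest reply is that the premise is inferred. Psychotherapy has its own recording instruction, and the visit form's instructions are not in the documents. Sites may never enter sessions as mental-health visits. That stands: inclusion is the plain reading, not an explicit rule.

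Second, totals are formed by type of service, so the natural reading is one comparison per type. Sessions cannot enter the primary-care or emergency totals. The overall number is named in the by-visit summary, and whether it is also tested is unclear. That stands too, and it limits the point to the mental-health total and any overall total.

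Third, the protocol does not prove that attendance is constant. Stopping therapy is only a potential withdrawal reason, and Protocol 9.3.4 expects some patients to start or stop. This weakens the claim only a little: the protocol intends the schedule not to change, and the test excludes patients who discontinue early.

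Fourth, the simulation uses three post-baseline monthly reports, whereas SAP 5.3.3 totals across all study visits. Adding the baseline month hardly changes the relative loss.

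Fifth, the summaries by reason could show a fall in crisis visits descriptively. They could, but without a comparison between arms.

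A reader might go further and infer that the test mainly sorts patients by psychotherapy status and loses most of its power. The documents do not support that as a general statement. It needs frequent or varied sessions, few other visits and a share near the middle of the range, and none of these is stated. Nor do they support calling this the only test of the functional-impairment objective, since no text maps exploratory endpoints to objectives.

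**Conclusion.** The point holds in a limited form. On the plain wording, the tested mental-health total, and any overall total, includes a potentially large component that treatment is not meant to change. Counting it dilutes a real effect and does not create a false one.

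The direction follows from the text, given that reading. The size rests on assumptions: 75 per arm, about 80% power without the sessions, and two or three other visits in 12 weeks. Under these, power is about 25–42% with weekly sessions and 30–70% of patients in psychotherapy, about 63% with weekly sessions at a 10% share, and about 56–71% with monthly sessions at 30–70%. More frequent other visits make the loss smaller.

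Severity is minor. The analysis is exploratory, no power is claimed for it, type I error is intact, and no confirmatory conclusion depends on it.

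**What to change.** In SAP 5.3.3, before unblinding:

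1. State whether ongoing scheduled psychotherapy sessions count as mental-health visits.
2. Test the mental-health total, and the overall total if it is tested, with those sessions removed. Identify them from the visit reason or the eCRF psychotherapy record. Keep unscheduled and crisis mental-health visits in the count.
3. Report the sessions separately by arm.
4. If sessions cannot be identified, replace the Mann-Whitney test for these totals with a van Elteren test stratified by psychotherapy at baseline. It costs almost nothing if sessions were never counted, but it recovers only part of the loss if session frequency varies between patients. Removal is therefore the first choice.

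The cost is a few sentences and a filter or stratum on data already collected. The one downside is that the coding of scheduled sessions has to be agreed while the data are still blinded.
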